The central hypothesis motivating this study is that remote patient monitoring (RPM) of infectious disease patients can efficiently facilitate self-isolation. Additionally, RPM can assist in more rapid identification of patients at risk, facilitate detection of patient deterioration, and enable early interventions, all of which play a vital role in resource utilization and outcomes.

Specific Aims

Aim-I **To develop and test a clinical care pathway that can be utilized in similar epidemic conditions in the future**. To study this aim, we will be using the COVID-19 medical surge as a condition to evaluate the framework of delivering care through remote patient monitoring. The success of this care delivery model will be evaluated on ease of model implementation, patient satisfaction, clinical outcomes, and the utilization of shared decision making.

Aim-II **To evaluate remote patient monitoring for appropriate resource utilization in epidemic and pandemic conditions**. To evaluate this aim, we plan to compare the emergency department (ED) visits and inpatient admission of patients with and without wearable remote patient monitoring devices. Additionally, we will compare the number of patients that required critical interventions (mechanical ventilation and ECMO) during the hospital stay.

Aim III **To evaluate the utilization of wearable technology for upfront predictions of patients that would require inpatient admissions.** To evaluate this aim, patients who are diagnosed with COVID-19 and are undergoing self-quarantine will be closely monitored using a wearable device, and sharedclinical decisions will be made based on the monitored data and patient diary. The comparison group will be patients undergoing routine standard of care at the hospital. ED visits, inpatient hospital admissions, and patient satisfaction will be the outcome measures compared between the two groups.

Aim IV To evaluate the association between early identification of critical, abnormal vital signs and the prevention of serious adverse events. To evaluate this aim, patients in the monitored group and non-monitored group will be compared for ED visits, inpatient admissions, length of hospital stay, and serious adverse events.

Objectives

The primary purpose of the study is to compare the number of inpatient admissions between the monitored and non-monitored patients.

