The secondary endpoints are to compare the number of ED visits, length of stay, patient satisfaction, the incidence of mechanical ventilation, ECMO, and serious adverse events (events requiring extended hospital stay).

Methods

In this prospective observational study, we are planning to recruit COVID-19 positive patients visiting emergency rooms (ER) associated with Montefiore Medical Center

Inclusion Criteria

- Diagnosis of COVID-19 (first-time COVID-19 diagnosis)
- Able to read and understand English

- Able to navigate and fulfill tasks on an electronic tablet
- 21 years and older
- Patients that do not require an inpatient admission as per the treating physician
- Patients who are insured through Medicare
- Patients who are staying in the same household for at least 15 days

Exclusion Criteria

- Have never used a mobile phone or tablet in the past
- Patients with an implanted pacemaker
- Patients with a diagnosis of hyperhidrosis
- Acute allergic reactions to the patches
- Confirmed diagnosis of psychiatric illness or anxiety disorder
- All private insurance patients

Recruitment Strategy

Every day around 4 pm, the research team will generate a list of patients who were tested COVID-19 positive and are discharged from ER without requiring inpatient admission. This list will include all the COVID-19 positive patients from all the emergency departments associated with Montefiore Medical Center. The potential patient list will be generated on every alternate day; for example, the list will be generated on (Monday, Wednesday, and Friday). We are only planning to enroll 5-6 patients on a single day. Alternate day enrollment will potentially allow us to have a balance in the number of patients in the intervention and the control group. Also, it helps us to streamline the study logistics. After screening for inclusion and exclusion criteria, the research team will identify potential patients eligible for the study.

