Monitoring will be prematurely terminated if the patient requires inpatient hospitalization; in all other cases, monitoring will be continued for fourteen days. During the monitoring period, patients will have the opportunity to call and speak to the medical professional at the Monitoring Intervention Center and also can call 911 in case of a severe emergency. Additionally, submitted is the guidelines put together by IMagineMic regarding the treatment and transfer of COVID-19 patients from home to the emergency (Appendix-2)

The patients will be remotely monitored for their vital signs such as blood pressure, heart rate, SPO₂, skin temperature, respiratory rate, two lead ECG, and accelerometer.

All the collected physiologic data will be transmitted to a central monitoring station where it will be evaluated continuously by licensed healthcare workers (MD, RN, and NP) who will provide real-time support to the patients. Also, the research team will obtain all the data points for future analytic purposes. Additionally, the research team will conduct a 30 day follow up phone call to catch information needed in case subjects end up visiting an outside institution.

Control Group

In this study control group will be patients those patients who are COVID positive and discharged from the ER and are not contacted by the study team during the same study period. In order to avoid chronological bias, it is essential to have controls from the same period as in the intervention group. The standard of care, the presentation, and the outcome of the disease are very much different in the surge phase of the COVID when compared to post surge months. Hence it is crucial to avoid chronological bias when comparing intervention and control groups. Additionally, in terms of evaluating the efficacy of the intervention, using patients from the surge period as a control group could potentially impact the conclusion of the study.

Regarding the care given to the control patients, Montefiore Emergency Department has a standard of operating protocols for patients discharged from the emergency room. All the usual standard of care available for the patients discharged from the emergency room will be provided to the patients, including telephone consultations. The study team will not interfere or dictate the care provided to the control patients.

Technology

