The first DSMB meeting will be conducted after the completion of 50% of the enrollment. The safety of the RPM will be the only outcome discussed during the DSMB meetings. Additionally, all the adverse events associated with the RPM will be reported to the DSMB and the IRB. In the event of serious adverse events, the termination or the continuation of the study will be at the discretion of the IRB. No interim analysis will be conducted, and the efficacy of the study will not be discussed at the DSMB meetings.

Statistical Analysis

[figure not shown]
In this prospective observational study, we are evaluating the efficacy of continuous monitoring in preventing inpatient admissions. A sample size of 300 patients is targeted for enrollment; 150 in the monitoring and 150 in the non-monitoring group. The sample size calculation is based on the hypothesized reduction of 10% inpatient admission between the two groups; 15% admission in the non-monitoring group, 80% statistical power, and 20% type –II error.

All continuous variables will be summarized using the following descriptive statistics: mean, standard deviation, median, maximum, and minimum. The frequency and percentages will be reported for all categorical variables. No interim analysis will be performed. Quantitative variables will be compared using parametric or non-parametric t-test. A Chi-square test will be used for the comparison of categorical outcomes. All significance tests will be two-tailed, and values of P <0.05 will be considered statistically significant.

Risks and Benefits

Risks associated with this study are minimal. Complications from pulse oximeters and the LifeSignal Biosensor 1AX* are exceedingly rare. Complications that may occur in this study include feeling a small pinch when the monitors are placed and perhaps a small irritation to the skin. Subjects will be asked to provide personal information (PHI). All attempts will be made to keep the PHI confidential within the limits of the law. All the study documents will be kept in a locked file cabinet in the research office. Electronic files will be password protected. Informed consent will clearly state that by participating in this study, the patient's personal information will be shared with an external monitoring agency.

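### Aim III asks whether wearable data predict admission, but its planned group comparison contains no predictor; Aim IV's comparison can address monitoring as a package, not early detection of abnormal vital signs.

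*Combined protocol and SAP*

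**What the plan says.** Under Specific Aims, Aim III is "To evaluate the utilization of wearable technology for upfront predictions of patients that would require inpatient admissions". Monitored patients have care decisions informed by their device data and diary, the comparator is routine standard of care, and "ED visits, inpatient hospital admissions, and patient satisfaction will be the outcome measures compared between the two groups".

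Aim IV is "To evaluate the association between early identification of critical, abnormal vital signs and the prevention of serious adverse events". Its evaluation is that "patients in the monitored group and non-monitored group will be compared for ED visits, inpatient admissions, length of hospital stay, and serious adverse events".

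The Objectives section lists a primary and several secondary endpoints, all of them comparisons between the two groups. Statistical Analysis gives descriptive summaries, a parametric or non-parametric two-group test for quantitative variables, and this: "A Chi-square test will be used for the comparison of categorical outcomes". It names no predictor, no accuracy measure and no analysis linking a vital-sign abnormality, or its timing, to an outcome.

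Two places foresee other uses of the monitoring data. External Monitoring says that "the research team will obtain all the data points for future analytic purposes", and Data Collection and Storage says that de-identified continuous data go to another team for further analysis. Neither gives a method or a link to an aim.

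**The concern.** A claim of prediction needs a predictor, an outcome, and a measure of how well one anticipates the other in the same patients. Aim III's planned comparison has only the outcome, split by group. If admissions fall, the report could say that the wearable predicts admission; if they do not, that it fails to predict. Neither conclusion would follow.

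Aim IV names early identification of abnormal vital signs as the exposure, but the variable compared is membership of the monitored group. A difference in serious adverse events could come from early detection, from ready access to clinicians, from reassurance, or from differences between patients who agreed to take part and patients who were never contacted.

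This matters because the protocol's background section presents the lack of predictive measures, and of a valid risk stratification tool, as a reason for the study.

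**Working it through.** **The plan's own figure.** Inputs from Statistical Analysis: 15% admitted in the non-monitoring group, a 10% reduction, 80% power, two-sided 0.05, 150 per group. Read as absolute, this is 15% versus 5%, with mean 10%. The pooled two-proportion formula gives

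n = [1.96·√(2·0.10·0.90) + 0.842·√(0.15·0.85 + 0.05·0.95)]² / 0.10² = (0.832 + 0.352)² / 0.01 ≈ 141 per group.

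At 150 per group the power is 82.6% by the normal approximation and 79.7% by Fisher's exact test, so 150 is consistent with its inputs. A relative reading (15% versus 13.5%) would need 8,525 per group, so the absolute reading is taken. The trial is therefore sized for a difference in admission rates and for nothing about prediction.

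**What the planned test can see.** Take 8 of 150 monitored and 22 of 150 non-monitored patients admitted, close to the planned rates (150 × 0.05 = 7.5; 150 × 0.15 = 22.5). Two hypothetical worlds:

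- World A: 6 of the 8 monitored admissions were preceded by a recorded abnormality; sensitivity 6/8 = 75%.
- World B: none was; sensitivity 0/8 = 0%.

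Both give the same table (8 and 142 against 22 and 128), hence the same chi-square statistic and p-value. The comparison carries no information that separates them.

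**Aim IV, exposure against analysis.** The aim's exposure is early identification of abnormal signs. The analysis variable is monitored or not. No definition of an abnormal sign or of early detection appears. Control Group describes usual care without study interference, and no collection of vital signs by the study is described for controls. The exposure therefore cannot be compared between the groups as written.

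**What a within-group analysis could deliver.** Expected monitored admissions are 150 × rate. The exact (Clopper-Pearson) 95% limits for x of n are the 2.5% quantile of Beta(x, n − x + 1) and the 97.5% quantile of Beta(x + 1, n − x). The values of x are illustrations, not forecasts.

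| Monitored admission rate | Expected admissions (90% range) | Illustrative sensitivity | Exact 95% CI |
|---|---|---|---|
| 5% (hypothesised) | 7.5 (3 to 12) | 6/8 = 75% | 35% to 97% |
| 5% (hypothesised) | 7.5 (3 to 12) | 8/8 = 100% | 63% to 100% |
| 15% (no effect) | 22.5 (16 to 30) | 18/22 = 82% | 60% to 95% |

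Even a perfect 8 of 8 leaves a lower limit of 63%.

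**The case against.** Five points can fairly be made on the other side.

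1. Aim III can be read as an evaluation of *using* the wearable: decisions are guided by its data, and outcomes are compared with usual care. That is a legitimate impact question, and the group comparison addresses it. This stands, and is why the comparison should be kept. It does not cover the prediction wording, and impact is already the subject of Aim II and the primary objective.

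2. A reader might infer that neither Aim III nor Aim IV has any relevant evidence behind it. The documents do not support that. Aim IV concerns prevention of serious adverse events, and these are compared between the groups; the central hypothesis names early detection as one mechanism of monitoring. The comparison bears on the package and stops short of the component.

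3. Further analysis of the monitoring data is foreseen. True, but with no method and no tie to an aim, it does not fill the gap.

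4. An accuracy analysis may have nothing ready to use. Technology says that alerts are issued when an intervention is needed, under supervision by licensed professionals. No alert threshold appears in the text, and the two appendices on monitoring and transfer are not in the material reviewed. Nor is it said that alert times are stored. It would be wrong to assume that a rule and log exist, so the remedy must be conditional.

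5. Staff act on the data and can arrange an ambulance, so an alert may cause an admission or avert one. Accuracy figures are then distorted, and listing alert-triggered admissions separately does not recover those averted. This also stands; it limits what may be claimed but does not make the group comparison a test of prediction.

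**Conclusion.** The concern holds for Aim III: the stated analysis does not fit the stated question, and no other section supplies one that does. For Aim IV it holds in a narrower sense: the analysis is usable, but the aim claims more than the analysis can show.

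The primary objective, the sample size and the error rate are untouched. No listed endpoint claims predictive accuracy, so this is a change that should be made rather than one on which the trial's validity turns.

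The size of the problem is best put as precision. With sensitivities of about 75% to 82%, the 95% interval would be about 62 percentage points wide at a 5% admission rate (97 − 35) and about 35 at 15% (95 − 60). This assumes the absolute reading of the 10% reduction, 150 evaluable monitored patients, and the illustrative counts above.

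**What to change.** **Aim III.** Keep the group comparison and label it the impact analysis. Add a prespecified analysis within the monitored group, for estimation only:

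- Predictor: the monitoring centre's documented alerts, if a rule and a time-stamped log exist. Otherwise, a definition of vital-sign abnormality for analysis purposes, fixed before outcomes are examined and applied to the stored data.
- Outcome: later inpatient admission, which is already the primary endpoint.
- Report: sensitivity, specificity and positive predictive value with exact 95% CIs, and the time from first abnormality to admission.
- Caveat to print with the results: care acted on these data, so alerts may have caused or averted admissions and the figures are distorted. List alert-triggered admissions descriptively.
- Expected precision: state it in advance for both the 5% and the 15% scenario.

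If no such predictor can be defined, restate Aim III as the effect of monitoring-guided care and draw no conclusion about prediction.

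**Aim IV.** Restate it as the association between being monitored and serious adverse events, subject to confounding. Draw no conclusion about early abnormal vital signs from the group comparison.

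**Cost.** Revised wording for two aims, a check with the monitoring company on whether an alert rule and log exist, and one extra analysis. Vital-sign data and admissions are already to be collected. The downside is that the limits for Aim III will be visibly wide.

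### Length of stay exists only for patients admitted later, so testing it between groups compares small subsets selected by the primary outcome, with bias in either direction

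*Combined protocol and SAP*

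**What the plan says.** Under Inclusion Criteria, the study takes "Patients that do not require an inpatient admission as per the treating physician", and recruitment works from lists of people already sent home from the emergency room. The primary purpose, under Objectives, is to "compare the number of inpatient admissions between the monitored and non-monitored patients".

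Length of stay appears in two places. The secondary endpoints "compare the number of ED visits, length of stay" along with other outcomes. Under Aim IV the two groups are to be "compared for ED visits, inpatient admissions, length of hospital stay, and serious adverse events".

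The Statistical Analysis section has one rule that could apply: "Quantitative variables will be compared using parametric or non-parametric t-test". It does not say which patients enter the length-of-stay comparison, what value a never-admitted patient receives, or how a death in hospital is handled.

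The planning figures in the same section are "150 in the monitoring and 150 in the non-monitoring group", "15% admission in the non-monitoring group" and a "hypothesized reduction of 10% inpatient admission between the two groups".

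**The concern.** Nobody has a hospital stay at entry. A stay is created by a later admission, and admission is what monitoring is meant to change. A test of length of stay among those admitted therefore compares two groups formed after baseline by the primary outcome. Perfect baseline balance would not make them comparable. Nor would the non-parametric option, because the problem is who is compared and not the shape of the distribution.

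If monitoring prevents mainly shorter stays, the monitored patients who are still admitted have longer stays on average, and monitoring seems to prolong hospitalisation. If it prevents mainly longer stays, the comparison exaggerates its benefit. An early death in hospital would also count as a short, apparently favourable stay.

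At stake is how one secondary endpoint and part of Aim IV are interpreted. The primary analysis and the sample size are not affected.

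**Working it through.** **Inputs from the Statistical Analysis section.** 150 patients per group; 15% admission in controls; a 10% reduction, read as absolute (15% to 5%); 80% power; two-sided 0.05.

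**The plan's own figure.** With mean proportion 0.10, the pooled formula is

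n = [1.96 × √(2 × 0.10 × 0.90) + 0.842 × √(0.15 × 0.85 + 0.05 × 0.95)]² / 0.10² = (0.832 + 0.352)² / 0.01, about 141 per group.

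At 150 per group the same approximation gives 82.6% power, and Fisher's exact test gives 79.7%. So 150 is consistent with 15% versus 5%. A relative reduction of 10% (15% to 13.5%) would need 8,525 per group, so the absolute reading is the right one.

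**Expected number of stays.** Control: 150 × 0.15 = 22.5 (95% binomial range 14 to 31). Monitored: 150 × 0.05 = 7.5 (range 3 to 13).

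**Precision of an admitted-only test.** Detectable difference at 80% power = (1.96 + 0.842) × √(1/22.5 + 1/7.5) = 2.80 × 0.422 = 1.18 SD. The t-based value for 22 versus 8 patients is 1.20 SD. Power for a 0.5 SD difference is about 22%.

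**Direction of the bias.** The documents give no distribution for length of stay, so the following is assumed: lognormal, median 5 days, log-SD 0.8; two-thirds of admissions prevented; no effect on the remaining stays; no deaths or dropout. Let r be the correlation between log stay and the tendency to be admitted despite monitoring.

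- Control mean = 5 × exp(0.8²/2) = 6.9 days.
- Monitored mean among admitted = 6.9 × 3 × Φ(0.8r − 0.431), where 0.431 is the normal quantile at 2/3.
- Hospital days per patient in the whole group = admission rate × mean stay. For controls this is 0.15 × 6.89 = 1.03.

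| Which stays are prevented | r | Mean among admitted, control vs monitored (days) | Days per patient, whole group |
|---|---|---|---|
| Mostly longer | −0.5 | 6.9 vs 4.2 | 1.03 vs 0.21 |
| Unrelated to length | 0 | 6.9 vs 6.9 | 1.03 vs 0.34 |
| Mostly shorter | 0.5 | 6.9 vs 10.1 | 1.03 vs 0.50 |
| Only the shortest (extreme) | 1 | 6.9 vs 13.3 | 1.03 vs 0.67 |

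**Simulated trials, same assumptions.** For r = 0, 0.5 and 1, the monitored admitted-only mean was the longer one in 45%, 82% and 99% of trials. Total monitored hospital days were nevertheless lower in 98%, 92% and 81%. The admitted-only rank test was significant towards longer monitored stays in about 3%, 22% and 82% of trials.

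**The case against.** Four objections carry weight.

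1. **The plan is silent; it does not specify the wrong analysis.** It never restricts the comparison to admitted patients, and scoring never-admitted patients as zero is not excluded. This is true. Admitted-only is still the natural reading of length of hospital stay, and leaving the choice open until the data are seen is itself a weakness.

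2. **The sign is not known.** A reader might infer that success on admissions will make monitoring look harmful. The documents do not support that. They hypothesise earlier identification and intervention, and nowhere say that the milder stays are the ones prevented. The Significance section expects shorter hospital stays and less need for advanced therapies, which fits prevention of severe stays at least as well. The bias would then favour monitoring. The 82% figure requires that exactly the shortest two-thirds of stays are prevented.

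3. **The reach is limited.** A reader might take length of stay to be an Aim II measure. Aim II lists ED visits, admissions and critical interventions; only Aim IV and the secondary endpoints name length of stay.

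4. **The alternative is not free or powerful.** Under External Monitoring, the 30-day call exists to catch visits to other institutions. No such call is described for controls, who by definition are not contacted by the study team. Scoring zero for any admission not found could therefore hide control admissions and bias against monitoring. This stands and limits the remedy, but the primary endpoint and the present length-of-stay endpoint have the same gap.

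**Conclusion.** The concern holds in a limited form. As the plan stands, the natural length-of-stay test compares about 22 with 7 to 8 patients selected by the primary outcome. It can detect only differences of about 1.2 SD, and its direction of bias depends on which admissions monitoring prevents. Against a control mean of 6.9 days, the monitored mean ranges from 4.2 to 13.3 days although monitoring changes no remaining stay. Hospital days over the whole group fall in every scenario.

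The patient counts follow from the plan's own rates. The day figures rest on the assumed lognormal distribution, the two-thirds prevention and the range of r, and they illustrate the mechanism without predicting a result. The effect of in-hospital deaths has not been quantified. This should be corrected before analysis, but it concerns one secondary endpoint only.

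**What to change.** In the Statistical Analysis section, replace length of stay as a between-group endpoint with total hospital days within 30 days of ED discharge, in all 300 patients, summed over admissions and zero for those never admitted. State a rule for death; days alive and out of hospital to day 30, with death scored as worst, is one option. Report the mean difference with a bootstrap 95% confidence interval. Report length of stay among admitted patients by group as description only, without a p-value.

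Ascertain admissions, discharge dates and deaths from the same source in both groups, for example institutional records. Information found only through the 30-day call should not enter the comparison unless an equivalent exists for controls.

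**Cost.** No extra patients: a paragraph of analysis text and a decision on ascertainment. It is not purely a wording change, because 30-day vital status and admission data for controls need a named source.

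**Limits.** Under the assumptions above, simulated power for the mean difference is modest: about 18% to 21% if only the shortest stays are prevented, and 61% to 65% if prevention is unrelated to length. A rank test over all patients reaches roughly 79% to 85%, but it agreed with the chi-square test on admission in 96% to 99% of trials and so largely repeats the primary endpoint. The change removes selection by admission; it does not remove baseline differences between groups that were not randomised.

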Lack of these predictive measures forces our healthcare system to adopt a "one-size-fits-all" model, which is inefficient, prohibitively expensive, and clinically ineffective in too many patients. As in the case of COVID-19, lack of a valid risk stratification tool and the possibility of the rapid deterioration of symptoms warrant continuous monitoring of non-hospitalized patients during their symptomatic phase. (18) The use of RPM could be instrumental in understanding and developing an algorithm for escalation of care and therapeutic interventions in our patient population. Moreover, during the medical surge, resource utilization is one of the pivotal strategies that must be considered in epidemic and pandemic preparedness. Appropriate resource utilization is essential to provide quality care to every patient and to mitigate the adverse outcomes associated with pandemics. The 4 "S' s," staff, stuff, space, and systems are the critical factors in pandemic preparedness and resource utilization.

COVID-19 in the minority population

It is readily apparent that our minority and lower socioeconomic populations are significantly more vulnerable in this pandemic. COVID-19 has been shown to have higher mortality rates among the African-American and Hispanic populations. (19) The Bronx represents one of the most diverse populations in the country and has been profoundly affected by COVID-19. An ability to monitor patients in an out-patient setting with wearable technology has the potential to address some of the historical obstacles to timely healthcare access for our patient population. The use of continuous monitoring would allow us to understand the progression of SARS-CoV-2 in our community while providing a mechanism for intervention. Whereas our patients may be less likely to seek medical attention, the use of RPM allows the medical facility to maintain a level of monitoring and provide a safety net in the event of clinical deterioration.

Utilization of wearable patches for remotely monitoring COVID-19 patients

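### Serious adverse events are defined only by hospital stay and no endpoint names death, so Aim IV can omit the most serious event and admissions have no death count beside them

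*Combined protocol and SAP*

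**What the plan says.** The primary comparison is inpatient admissions (Objectives). The secondary endpoints are ED visits, length of stay, patient satisfaction, mechanical ventilation, ECMO and "serious adverse events (events requiring extended hospital stay".

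Under Aim IV, "patients in the monitored group and non-monitored group will be compared for ED visits, inpatient admissions, length of hospital stay, and serious adverse events". Aim II ties the critical interventions to a hospital stay: it will "compare the number of patients that required critical interventions (mechanical ventilation and ECMO) during the hospital stay". Aim I adds clinical outcomes as a criterion of success without saying which ones. The Statistical Analysis section adds no further endpoint.

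Three other places bear on whether a death would be seen:

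- DSMB: "all the adverse events associated with the RPM will be reported to the DSMB and the IRB".
- External Monitoring: the research team makes a "30 day follow up phone call to catch information needed in case subjects end up visiting an outside institution". Vital status is not mentioned.
- Control Group: controls are patients who "are not contacted by the study team during the same study period".

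Mortality is discussed in the background sections but does not reappear among the aims or endpoints.

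**The concern.** The background justifies monitoring on the ground that late recognition of deterioration raises mortality. Aim IV then asks whether early recognition prevents serious adverse events, but the definition it uses requires a longer hospital stay. A death that produces no such stay falls outside it.

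The second stake is how the primary result is read. Success means fewer admissions. A reader will want to know whether admissions fell because patients did better or because some deteriorated without reaching the hospital. Deaths by group are the simplest check, and the plan does not produce them.

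**Working it through.** **1. Scoring under the plan as written.** ED visit means a visit after the index discharge.

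| Endpoint | Recovers at home | Dies, no hospital contact | Dies after admission |
|---|---|---|---|
| Inpatient admission (primary) | no | no | yes |
| ED visit | no | no | depends on route |
| Hospital days | none | none | possibly few |
| Ventilation, ECMO | no | no | only if used |
| Serious adverse event | no | no | not necessarily |
| Satisfaction | obtainable | missing | missing |

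The first two columns agree on every event endpoint and differ only in the missing satisfaction score. The third column is not lost from the primary, but an early death need not involve an extended stay, so it can be absent from the serious adverse event count.

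**2. The plan's own sample size.** Inputs from Statistical Analysis: 150 per group, 15% admissions in controls, a 10% reduction, 80% power, two-sided 0.05. Read as absolute, the reduction gives 15% vs 5%. (Read as relative, 15% vs 13.5%, the formula below needs 8,525 per group, so the absolute reading is the workable one.)

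n = [1.96 × √(2 × 0.10 × 0.90) + 0.8416 × √(0.15 × 0.85 + 0.05 × 0.95)]² / 0.10² = 140.1, so 141 per group.

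Power at 150 per group by the same formula is 82.6%. The stated 150 is not reproduced exactly but is on the generous side. The point here does not depend on it.

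**3. How many uncounted deaths would change the primary.** Expected admissions are 150 × 0.15 = 22.5 and 150 × 0.05 = 7.5, rounded to 23 vs 8. For 150 per group with a and b events and E = a + b, the uncorrected chi-square is 300(a − b)² / [E(300 − E)]. Add deaths without admission to the monitored group only, the least favourable case:

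| Control vs monitored | Deaths added | Chi-square | p |
|---|---|---|---|
| 23 vs 8 | 0 | 300 × 225 / (31 × 269) = 8.09 | 0.004 |
| 23 vs 12 | 4 | 300 × 121 / (35 × 265) = 3.91 | 0.048 |
| 23 vs 13 | 5 | 300 × 100 / (36 × 264) = 3.16 | 0.076 |

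Five are needed, with none in controls.

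**4. Direction.** The effect can go either way. With illustrative borderline counts, one monitored death turns 22 vs 11 (p = 0.042) into 22 vs 12 (p = 0.069), and one control death turns 20 vs 10 (p = 0.054) into 21 vs 10 (p = 0.037).

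**5. What a death count could show.** The documents give no death rate. Assuming 0.5% to 2% for all deaths, in or out of hospital, gives 150 × 0.005 = 0.75 to 150 × 0.02 = 3 per group. With 0 of 150, the exact 95% upper limit is 1 − 0.025^(1/150) = 2.4%. With 3 vs 0, the difference is 2.0 points (Newcombe 95% CI −0.8 to 5.7). Power for 2% vs 0.5% is about 18%. Only some of these deaths would lack an admission, so this range must not be used as the rate of uncounted deaths in step 3.

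**The case against.** The strongest reply is that the primary is barely touched. That stands: it takes five uncounted deaths, all in one group, to overturn the planned effect. The borderline examples show direction only, since any single event can tip a p-value near 0.05.

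A second reply is that deaths in the monitored group are unlikely to go unseen. The Technology section describes round-the-clock supervision by licensed staff, alerts and ambulance support, and the DSMB section makes the safety of monitoring the board's only topic and links study continuation to serious adverse events. This also has weight. But reporting covers events associated with the monitoring, which gives no count for controls and therefore no comparison.

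A third is that clinical outcomes in Aim I may be meant to include death. It may, but the term is undefined and is not carried into the endpoint list.

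A reader might infer from the remark that "our patients may be less likely to seek medical attention" that the protocol itself expects deterioration without hospital contact. The documents do not support that much. The remark concerns the community served, the same sentence presents monitoring as a safety net, and every study patient has already come to an emergency room. It is weak support at most for controls and points the other way for monitored patients.

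**Conclusion.** The gap is real and rests on the text alone: the serious adverse event definition depends on hospital stay, and no listed endpoint counts death. The damage is to Aim IV and to the safety reading of fewer admissions.

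Two stronger conclusions might be inferred, and neither is supported. One is that the primary result would be unreliable. At 15% vs 5% with 150 per group it withstands four uncounted monitored deaths with none in controls (p = 0.048). The other is that the omission favours monitoring. An uncounted monitored death flatters it, but an uncounted control death hides a benefit, and nothing in the documents says which is more likely.

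No probability of a changed conclusion can be given, because that needs the rate of deaths without admission in each group, and the documents supply no death rate at all. The change should be made, but it does not put the main comparison in doubt.

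**What to change.** 1. Include death from any cause, in or out of hospital, in the serious adverse event definition. Report 30-day deaths in each group over all enrolled patients (150 planned per group) as counts with confidence intervals, with no claim of power.
2. Keep inpatient admission as the primary and add admission-or-death within 30 days as a sensitivity analysis. The primary and its sample size are unchanged.
3. Ascertain day-30 vital status by the same method in both groups, and report patients with unknown status by group. Reconcile the 30-day call with the definition of controls as patients the study team does not contact; the documents do not say whether controls receive it. They also name no source for vital status, so the team has to identify one.

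The cost is a revised definition, one extra analysis and a modest day-30 check on 300 patients. Control data will need access approval, because the Recruitment Strategy section describes consent only for patients the team calls. On the assumed rates few deaths are expected, so the death comparison will be descriptive. The change is best made before enrolment, since adding death once results are known would look post hoc.
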